8.4 Duration of therapy

All further doses of daratumumab may be administered as described in section 8.1, however patient will be considered “off-study” after the pre-defined follow-up period.

8.5 Duration of follow-up

Patients will be followed for 4 weeks from the first accelerated infusion.

Patients removed from study for unacceptable adverse event(s) will be followed until resolution or stabilization of the adverse event.

8.6 Criteria for removal from study

If the patient suffers a grade 4 infusion reaction, the patient will be removed from the study.

9. DOSING DELAYS / DOSE MODIFICATIONS

Infusion reactions will be recorded as described in Appendix B.

9.1 Grade 1-2 infusion related reactions

At the time that this protocol was written, for daratumumab grade 1-2 infusion reactions, interrupt daratumumab. When symptoms resolve, start at the last tolerated rate for one hour and begin re-escalating the infusion rate as tolerated.

9.2 Grade 3 infusion related reaction

Follow institutional protocol. At the time that this protocol was written, for grade 3 infusion reactions, stop the infusion, treat medically, and restart at half the rate when symptoms improve to grade 0-1. Subsequent rate escalation is to occur at physician discretion.

9.3 Grade 4 infusion related reaction

Protocol accrual will be halted and the protocol modified.

10. PHARMACEUTICAL INFORMATION

A list of the adverse events and potential risks associated with daratumumab can be found in the FDA approved package inserts.

10.1 Daratumumab

Classification: fully human IgG1κ monoclonal antibody

Mode of Action: Daratumumab is an antibody directed against myeloma cell surface glycoprotein CD38 and inhibits tumor growth by 1) direct apoptosis through Fc mediated cross-linking and 2) immune-mediated cell lysis through complement dependent cytotoxicity (CDC), antibody dependent cell mediated cytotoxicity (ADCC), and antibody dependent cellular phagocytosis (ADCP).

Administration: Per protocol, see section 8.1

Dosing: For treatment of myeloma, dose of daratumumab is 16 mg/kg IV, see prescribing information for dosing schedule. Dose is calculated based on actual body weight.

How supplied: Commercially

Preparation/Handling/Storage: Daratumumab will be prepared aseptically according to local procedures. See manufacturer package insert or institutional protocol for proper handling and storage of the medication.

10.2 Dexamethasone

Classification: Corticosteroid

Mode of Action: Dexamethasone is a synthetic adrenocortical steroid with potent anti-inflammatory effects in disorders of many organ systems. It decreases inflammation by suppression of neutrophil migration, decreased production of inflammatory mediators, and reversal of increased capillary permeability.

Administration: Administer the 4 mg/mL or 10 mg/mL intravenously as an undiluted or diluted solution. Oral tablets at an equivalent dose may be substituted for IV.

Dosing: Per treating physician.

How supplied: Commercially

Preparation/Handling/Storage: Dexamethasone will be prepared according to local procedures. See manufacturer package insert or institutional protocol for proper handling and storage of the medication.

11. STUDY CALENDARS

Patients will be approached in the infusion suite for consent, generally within 4 weeks of day 1. Screening and first infusion can occur on the same day.

11.1 SCHEDULE OF EVENTS

Assessment	Screening	First accelerated infusion
Signed informed consent	X	
Inclusion/Exclusion Criteria	X	
Height and weight ^a	X	
Vital signs	X	X
Daratumumab administration		X
Record adverse events		X

12. STATISTICAL CONSIDERATIONS

12.1 General approach

The primary objective of this study is to assess the safety of administering Daratumumab over a shortened period of time following the first two standard doses. The primary endpoint is infusion-related reactions (IRR) assessed with the first dose using the accelerated dosing regimen. The incidence rate of IRR is defined and calculated as the number of patients with grade 3 IRR divided by the total number of patients who receive the accelerated dosing regimen.

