4. OBJECTIVES

Hypothesis	Objective	Endpoint
Infusing daratumumab will not be associated with any grade 3-4 infusion related reactions	Determine the safety and tolerability of decreasing the infusion time of daratumumab in patients that have already received 2+ doses of daratumumab and are continuing on Daratumumab	Analysis of AEs possibly, probably, or definitely related to protocol therapy will summarize infusion related grade 3-4 reactions.
Accelerated daratumumab infusion will significantly decrease the time patients spend waiting for daratumumab to infuse.	Estimate the time savings vs predicted infusion time	The start and stop times of daratumumab infusion will be tracked during infusion acceleration and the number of daratumumab infusions will be tracked from the time of consent until the last daratumumab infusion.

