12.2 Safety analysis

Simon's two-stage optimal design was used to design the study. Two previous trials SIRIUS (n=106) and GEN501 (n=42) reported no grade 3 IRR with the 3rd or subsequent infusions. Given this observed proportion of 0/148, the upper bound of a 95% binomial confidence interval is 0.02, which translates to the alternative hypothesis that a desirable safety rate is at least 98%.

Based on previous clinical experience with daratumumab at our institution, 15% or higher incidence rate of grade 3 IRR is not acceptable, which leads to a null hypothesis that the true safety rate is at most 85%. With a type I error probability of 0.05 and 80% power, Simon's two-stage optimal design allows an interim analysis after 7 patients are enrolled. If only 6 or fewer patients are grade 3 IRR-free, we will conclude the regimen is not safe enough and trial accrual will be halted and the protocol modified. If all 7 patients are grade 3 IRR-free, we will continue to accrue to a total of 28 patients.

Out of all 28 patients, if the total grade 3 IRR-free patients is ≤ 26 (i.e. 2 or more patient with grade 3 IRR), we will conclude the regimen is too toxic. In addition, if any grade 4 IRR is observed, the trial will be suspended temporarily, and the regimen

will be reevaluated and modified to alleviate safety concerns. If the regimen is indeed too toxic with true safety rate no higher than 85%, we will have a 68% chance of early termination at the interim analysis.

With anticipated accrual rate of around 5-6 patients each month, the accrual period will be less than 6 months to achieve our 28 total enrollment goal.

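### Sections 12.1 and 12.2 count only grade 3 IRR in the primary rate and stopping boundaries, so a grade 4 or 5 IRR is read as a non-event; the rate also has no planned interval

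*Combined protocol and SAP*

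**What the plan says.** - **Primary rate (12.1).** "The incidence rate of IRR is defined and calculated as the number of patients with grade 3 IRR", over all patients who receive the accelerated regimen. The endpoint is assessed at the first accelerated dose.
- **Unacceptable rate (12.2).** "15% or higher incidence rate of grade 3 IRR is not acceptable". The design tests a safety rate of at most 85% against one of at least 98%.
- **Stage 1 (12.2).** Accrual halts if 6 or fewer of 7 patients are free of grade 3 IRR. "If all 7 patients are grade 3 IRR-free, we will continue to accrue to a total of 28 patients".
- **Final rule (12.2).** The regimen is judged too toxic with "2 or more patient with grade 3 IRR" among 28.
- **Grade 4 in conduct.** Section 12.2 adds that "if any grade 4 IRR is observed, the trial will be suspended temporarily". Section 9.3 halts accrual and modifies the protocol. Section 8.6 takes the patient off study.
- **Objectives (Section 4).** The hypothesis reads "Infusing daratumumab will not be associated with any grade 3-4 infusion related reactions", and the analysis of related adverse events "will summarize infusion related grade 3-4 reactions".
- **Grading (Appendix B).** Grades 3, 4 and 5 are separate categories; grade 4 is life-threatening and grade 5 is death.
- **Interval.** The only one in the plan is for the historical 0/148, where "the upper bound of a 95% binomial confidence interval is 0.02". None is planned for the trial's own rate.

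**The concern.** In a safety trial the event that counts against the regimen should include everything at least as bad as the threshold. Section 4 is written that way; Sections 12.1 and 12.2 are not. Taken at their word, the most severe reactions lower neither the stage 1 count of IRR-free patients nor the final one, and they do not enter the reported incidence. An analyst who programs the endpoint as written would produce a rate and a pass/fail result that disagree with the Section 4 summary of the same patients.

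The second, smaller matter is precision. A reported 0% or 3.6% does not show how high a rate 28 patients leave open. If an interval is chosen only after the data are in, a passing 1/28 could be published beside an ordinary limit that includes the 15% rate the design has just rejected.

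**Working it through.** **1. The design reproduces.** Inputs from 12.2: unacceptable rate 15%, desirable rate 2%, 7 then 21 patients, continue with 0 events in 7, pass with at most 1 in 28. Let q be the true event rate.

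- Early stopping at q = 0.15: 1 − 0.85^7 = 0.679 (plan: 68%).
- Probability of passing: (1−q)^7 × P(Bin(21,q) ≤ 1).
- At q = 0.15: 0.0497 (plan: 0.05). At q = 0.02: 0.811 (plan: 80%).

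These depend only on the rate of whatever event is counted, so widening the event definition leaves the arithmetic alone if 15% and 2% are kept as the two rates.

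**2. What the numerator does.** The patterns below are illustrative. The documents give no grade 4 rate for this regimen, so no probability is attached. Each assumes the trial continues, or is reported, after the grade 4 review.

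| IRRs observed | Grade 3 only, as written | Grade 3 or higher |
|---|---|---|
| One grade 4 in the first 7 | 0/7, boundary says continue | 1/7, boundary says stop |
| 0 in 7, then one grade 4 in 21 | 0/28 = 0%, pass | 1/28 = 3.6%, pass |
| 0 in 7, then one grade 3 and one grade 4 in 21 | 1/28 = 3.6%, pass | 2/28 = 7.1%, fail |

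A grade 5 IRR would be treated in the count as grade 4 is here.

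**3. Interval for the trial's own rate.** A passing 1/28 can arise only as 0/7 then 1/21.

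- Stage-wise one-sided 95% limit: solve (1−q)^7 × P(Bin(21,q) ≤ k) = 0.05.
- Ordinary Clopper-Pearson one-sided 95% limit: solve P(Bin(28,q) ≤ k) = 0.05.

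| Result | Ordinary, one-sided 95% | Stage-wise, one-sided 95% |
|---|---|---|
| 0/28 | 10.1% | 10.1% |
| 1/28 (pass) | 15.85% | 14.98% |
| 2/28 (fail) | 20.8% | 18.8% |

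For 0/28 both equal 1 − 0.05^(1/28) = 0.101. The two 1/28 limits straddle 15% because the tail at q = 0.15 is 0.0627 for a single sample of 28 but 0.0497 for the two-stage design. Two-sided 95% upper limits for 1/28 are 18.3% (ordinary) and 17.5% (stage-wise), both above 15%, so naming the method without the level is not enough.

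The 1/28 pass is not rare. Its probability is 0.811 − 0.568 = 0.243 at a true rate of 2%, and 0.501 − 0.238 = 0.263 at 5%. That is how often the choice of limit matters, not a rate of wrong decisions.

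**4. Sensitivity to the achieved size.** With 27 evaluable patients (0/7 then 1/20), the stage-wise limit is 15.46%. The limit must therefore be computed for the stage sizes actually achieved.

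**The case against.** **A grade 4 reaction cannot go unnoticed.** That is right. Sections 12.2, 9.3 and 8.6 all respond to it, and Section 4 summarises it. A reader might infer that the plan would let a dangerous regimen through unseen; the documents do not support that. What remains is narrower. The suspension is temporary, and nothing in the plan puts the patient back into the numerator or the boundary count when the trial resumes or is reported.

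**'Grade 3' may be shorthand for severe.** Possibly, and the Section 4 grouping suggests that intent. But 12.2 names grade 4 separately from grade 3 in the same section, and Appendix B keeps the grades apart, so the literal reading is available and should be closed off.

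**The interval is optional.** This largely stands. The two-stage rule is the primary inference and is valid without one, and nothing forbids reporting one. A reader might take the 15.85% limit as evidence that a 1/28 pass is unsound. It is not: that limit ignores the interim look, and the conflict needs exactly 1/28 and an ordinary one-sided limit. A two-sided 95% limit above 15% does not contradict a one-sided 5% test either. The stage-wise limit agrees with the decision by construction, because it inverts the design's own test.

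**The historical 0.02 might seem to settle the level.** It does not. 0/148 gives 2.00% one-sided and 2.46% two-sided, and both round to 0.02. The case for one-sided rests on the design's one-sided 0.05 error rate.

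**Conclusion.** The numerator is wrong as written and should be corrected. Read literally, each patient with a grade 4 or 5 IRR lowers the reported rate by 1/28 = 3.6 percentage points and is absent from a boundary that fails at two events. In the patterns shown, this reverses the boundary result when the grade 4 falls in the first 7, or when it accompanies one grade 3 later.

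This rests on two assumptions: that the endpoint is analysed as worded, and that 15% and 2% are kept as the rates for grade 3 or higher IRR. The second fits the background in Section 5.2, which describes the reported reactions as non-life-threatening.

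The missing interval is a minor reporting improvement. It bears on how 0/28 or 1/28 is read, not on any decision. A reader might conclude that the sample size, boundaries or error rates are faulty; they reproduce, and they stand.

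**What to change.** 1. **Numerator and boundaries (main change).** In 12.1 and in the stage 1 and final rules of 12.2, replace 'grade 3 IRR' with 'grade 3 or higher IRR', consistent with Section 4. Leave the separate grade 4 suspension rule as it is.
2. **Interval (minor).** Add to 12.1 or 12.2: *The number and proportion of patients with grade 3 or higher IRR will be reported with an exact one-sided 95% upper confidence limit under stage-wise ordering, computed for the achieved stage sizes. The result will be described as compatible, at one-sided 95% confidence, with rates up to this limit.*

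**Cost.** A few words in 12.1 and 12.2, two added sentences and a few lines of code. Sample size, boundary values and error rates do not change. The downside is a less favourable-looking report: 0% with an upper limit of 10.1%, or 3.6% with an upper limit of 14.98%.

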12.2 Safety analysis

Simon's two-stage optimal design was used to design the study. Two previous trials SIRIUS (n=106) and GEN501 (n=42) reported no grade 3 IRR with the 3rd or subsequent infusions. Given this observed proportion of 0/148, the upper bound of a 95% binomial confidence interval is 0.02, which translates to the alternative hypothesis that a desirable safety rate is at least 98%.

Based on previous clinical experience with daratumumab at our institution, 15% or higher incidence rate of grade 3 IRR is not acceptable, which leads to a null hypothesis that the true safety rate is at most 85%. With a type I error probability of 0.05 and 80% power, Simon's two-stage optimal design allows an interim analysis after 7 patients are enrolled. If only 6 or fewer patients are grade 3 IRR-free, we will conclude the regimen is not safe enough and trial accrual will be halted and the protocol modified. If all 7 patients are grade 3 IRR-free, we will continue to accrue to a total of 28 patients.

Out of all 28 patients, if the total grade 3 IRR-free patients is ≤ 26 (i.e. 2 or more patient with grade 3 IRR), we will conclude the regimen is too toxic. In addition, if any grade 4 IRR is observed, the trial will be suspended temporarily, and the regimen

will be reevaluated and modified to alleviate safety concerns. If the regimen is indeed too toxic with true safety rate no higher than 85%, we will have a 68% chance of early termination at the interim analysis.

With anticipated accrual rate of around 5-6 patients each month, the accrual period will be less than 6 months to achieve our 28 total enrollment goal.

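### Does counting the Simon looks on enrolled rather than infused patients upset the 7/28 stopping rule?

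*Combined protocol and SAP*

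**What the plan says.** Section 12.2 sets out a Simon optimal two-stage design "With a type I error probability of 0.05 and 80% power". It has a "null hypothesis that the true safety rate is at most 85" per cent, and an alternative under which "a desirable safety rate is at least 98" per cent. It "allows an interim analysis after 7 patients are enrolled". The stage 1 rule is "If only 6 or fewer patients are grade 3 IRR-free", accrual halts; if all seven are free of grade 3 IRR, accrual goes on to 28. The final rule applies to all 28 patients: "if the total grade 3 IRR-free patients is ≤ 26 (i.e. 2 or more patient with grade 3 IRR"), the regimen is judged too toxic. The same section describes 28 as the enrolment goal.

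Section 12.1 assesses the primary endpoint at the first accelerated dose, and its denominator is the "total number of patients who receive the accelerated dosing regimen".

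Section 11 has patients approached in the infusion suite for consent, "generally within 4 weeks of day 1". The next sentence there allows screening and the first infusion on one day. Section 6.1.1 admits only patients who have had at least two infusions and have another scheduled.

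Neither section 12 nor section 7 says how a patient who enrols but never receives the accelerated infusion is counted, or whether that patient is replaced.

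**The concern.** Enrolled and infused are different populations whenever consent comes before treatment. If a patient is entered and then not infused, 12.2 read literally leaves two ways to score that patient, and both look bad.

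- **Scored as IRR-free.** The look rests on fewer infusions than the design assumed. Type I error is already at its limit, so it goes over 5%.
- **Not scored as IRR-free.** With seven enrolled, six infused and no reactions, only six patients are IRR-free, and the halt rule is met without any toxicity.

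The final rule is stated in two forms, and these can also part. With 27 infused and one reaction, 26 patients are IRR-free. The count of IRR-free patients then says too toxic, while the count of reactions says not.

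At stake would be a small trial whose conclusion turned on a scoring choice made after the data were seen. The trial is unblinded, and its investigators review the data themselves (section 12.3).

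**Working it through.** **Inputs, all from section 12.2.** Stage 1 has n1 = 7 and continues only with 0 grade 3 IRRs. The total is 28 (21 in stage 2), and at most 1 IRR is allowed overall. The IRR rate is 0.15 under the null and 0.02 under the alternative.

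**Formula.** With m1 and m2 patients infused in the two stages, the chance of declaring the regimen safe is P = (1−q)^m1 × P(Bin(m2, q) ≤ 1), where q is the IRR rate. The probability of early termination is 1 − (1−q)^m1.

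**The plan's own figures (7 + 21).**
- Early termination at q = 0.15: 1 − 0.85^7 = 1 − 0.3206 = 0.679, which is the stated 68%.
- Type I error: 0.3206 × (0.85^21 + 21 × 0.15 × 0.85^20) = 0.3206 × 0.1550 = 0.0497.
- Power: 0.98^7 × (0.98^21 + 21 × 0.02 × 0.98^20) = 0.8681 × 0.9347 = 0.811.

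A search over two-stage designs meeting the 5% and 80% limits returns 7/28 as optimal, with expected sample size 13.7 under the null.

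**One patient enrolled, never infused and not replaced.**

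| Reading | Infused | Type I error | Power | Early termination at 15% |
|---|---|---|---|---|
| As designed | 7 + 21 | 0.0497 | 0.811 | 0.679 |
| Stage 1 miss, left out or scored IRR-free | 6 + 21 | 0.3771 × 0.1550 = 0.0585 | 0.828 | 0.623 |
| Stage 2 miss, left out or scored IRR-free | 7 + 20 | 0.3206 × 0.1756 = 0.0563 | 0.816 | 0.679 |
| One miss in each stage, same scoring | 6 + 20 | 0.3771 × 0.1756 = 0.0662 | 0.833 | 0.623 |
| Stage 2 miss, not scored IRR-free | 7 + 20, no IRR allowed | 0.85^27 = 0.0124 | 0.98^27 = 0.580 | 0.679 |
| Stage 1 miss, not scored IRR-free | 6 | trial halts | trial halts | certain |
| Looks on infused patients, or patient replaced | 7 + 21 | 0.0497 | 0.811 | 0.679 |

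The dilemma is therefore not exhaustive. The last row is a third reading, and nothing goes wrong under it. In stage 2, not scoring the patient as IRR-free neither stops a toxicity-free trial (27 IRR-free still passes) nor raises type I error.

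**Which reading the text supports.** Under 12.1 a patient has an endpoint only after the first accelerated dose, and the denominator is recipients. Scoring a never-infused patient either way puts someone into the rule whom 12.1 leaves out. The stage 1 go condition needs seven known outcomes, which requires seven infusions. The final rule is stated over all 28 patients.

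**The two forms of the final rule.** With 28 assessed patients, 26 or fewer IRR-free means 28 − 26 = 2 or more reactions, so the forms are identical. They part only if the rule is applied to 27 infused patients, the missing patient is not scored IRR-free, and there is exactly one reaction. With 0 reactions, or with 2 or more, they agree.

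**How often.** The documents give no rate of non-infusion. Under assumed rates of 1%, 2%, 5% and 10%, the chance of at least one such patient among the first seven is 1 − (1−rate)^7 = 6.8%, 13.2%, 30.2% and 52.2%. If all such patients were scored IRR-free, type I error would be 0.0517, 0.0538, 0.0606 and 0.0737. If all were scored as failures, power would be 0.705, 0.602, 0.345 and 0.113.

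**Cost of replacing one patient.** At the slower stated accrual of 5 a month, 28 patients take 28/5 = 5.6 months and 29 take 29/5 = 5.8 months, still within the six months that 12.2 expects.

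**The case for a change.** The best case for a change is that the convention really is unwritten. Section 12.2 says enrolled, eligibility requires only that another dose be scheduled, and dosing eventually becomes monthly, so a consented patient could wait weeks and miss the infusion. One such patient could move type I error anywhere from 0.012 to 0.059, or power from 0.81 to 0.58, depending on a choice made with the results in view. One sentence would settle it.

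Part of this stands: the wording is loose, no replacement rule is given, and the arithmetic is right. The large swings do not carry over. The loss of power and the toxicity-free halt both need a never-infused patient to be counted as a safety failure. That contradicts the 12.1 denominator and the purpose of a rule whose stated conclusion is that the regimen is not safe enough. If 12.1 is followed, the only exposure left is stopping at 28 enrolled without replacement. For one patient that costs less than one percentage point of type I error (0.0585 − 0.0497 = 0.0088 at most). Recruitment in the infusion suite, among patients already receiving the drug and with same-day treatment allowed, makes even that uncommon, although the documents give no figure to prove it.

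**Conclusion.** No change follows. The mismatch between enrolled in 12.2 and recipients in 12.1 is real, but it is a gap that an analyst fills sensibly: count the first look on seven infused and assessed patients and the final one on 28, replace anyone never infused, and report those patients separately. Type I error is then 0.0497, power 0.811 and early termination 0.679, all as designed, and the two forms of the final rule coincide.

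This rests on reading 12.2 in the light of 12.1, and on non-infusion being uncommon. The second is a judgement from sections 6.1.1 and 11, not a documented rate. If the first assumption held but replacement were overlooked, one missing patient would bring type I error to 0.056–0.059, and one in each stage to 0.066. If never-infused patients were counted as failures the effect would be much larger, but the plan gives no support for that scoring.

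### Section 12.2 applies its grade 3 IRR boundaries only after 7 and after 28 patients; one added sentence would stop accrual once failure is certain (a cheap improvement, not a design error)

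*Combined protocol and SAP*

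**What the plan says.** Section 12.2 describes a Simon optimal design that "allows an interim analysis after 7 patients are enrolled". The stage 1 rule is "If only 6 or fewer patients are grade 3 IRR-free, we will conclude the regimen is not safe enough", in which case accrual halts and the protocol is modified. Otherwise, "If all 7 patients are grade 3 IRR-free, we will continue to accrue to a total of 28 patients". The final rule begins "Out of all 28 patients, if the total grade 3 IRR-free patients is" 26 or fewer, which the text restates as "2 or more patient with grade 3 IRR"; the regimen is then called too toxic.

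The only halt triggered by a single event is for grade 4: "if any grade 4 IRR is observed, the trial will be suspended temporarily" (12.2), with a matching accrual halt in 9.3. Section 9.2, on grade 3 reactions, covers the affected patient and is silent on accrual. Section 12.3 provides an investigator review at least once a month and lets the principal investigator (PI) judge whether to end the trial early. It gives no number of grade 3 events.

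The endpoint is "assessed with the first dose using the accelerated dosing regimen" (12.1), and 8.3 adds a 30-minute observation period after that infusion.

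**The concern.** Stage 1 passes only with 7 of 7 patients free of grade 3 IRR, so one event among patients 1-7 settles it. Stage 2 therefore starts with no events, and the second event among patients 8-28 settles the trial. The text applies both limits only when the stage is full. Read literally, it permits up to 6 more patients after failure is fixed in stage 1 (event in patient 1) and up to 19 in stage 2 (second event in patient 9; 28 − 9 = 19). These patients would receive the accelerated infusion when the test could no longer come out favourably. The plan has an immediate trigger for grade 4 but none for grade 3, which is its primary endpoint.

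**Working it through.** **Inputs.** From 12.2: unacceptable grade 3 rate q = 0.15, desirable rate q = 0.02, stage sizes 7 and 28, the two limits above, and accrual of 5-6 patients a month. The rate q = 0.05 is an intermediate value chosen for illustration. Let p = 1 − q.

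**1. The plan's own figures.**
- Early termination at q = 0.15: 1 − 0.85^7 = 0.679 (the plan states 68%).
- Probability of passing: p^7 × (p^21 + 21·q·p^20). At q = 0.15 this is 0.3206 × 0.1550 = 0.0497 (limit 0.05). At q = 0.02 it is 0.8681 × 0.9347 = 0.811 (target 0.80).
- An exhaustive search up to 44 patients also returns 7/28 with these limits as the optimal design.

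**2. Expected number of patients, as planned.** 7(1 − p^7) + 28p^7. At q = 0.15: 7 × 0.6794 + 28 × 0.3206 = 13.73.

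**3. Expected number if accrual stops when failure is fixed.** Σ(k=1..7) k·q·p^(k−1) + p^7 Σ(j=2..21) (7+j)(j−1)·q²·p^(j−2) + 28·P(pass). At q = 0.15:
- fail in stage 1: probability 0.6794, mean stop at patient 3.36, contribution 2.29;
- fail in stage 2: probability 0.3206 × 0.8450 = 0.2709, mean stop at patient 7 + 10.44 = 17.44, contribution 4.73;
- pass: 28 × 0.0497 = 1.39.

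The unrounded total is 8.40. The saving is 13.73 − 8.40 = 5.33 patients and 0.15 × 5.33 = 0.80 grade 3 IRRs. This is the upper bound, because it assumes that the 12.3 review stops nothing. Simulation gave the same expected numbers.

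**4. Allowing for the 12.3 review.** Assume that a review after every m patients always halts a trial that has already failed. A failed trial then stops at the next multiple of m, capped at 7 or 28. One month's accrual corresponds to m = 5 or 6; m = 3 represents more frequent review. Patients saved by the added sentence:

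| True grade 3 rate | Planned v stopped at boundary, no review | Saved, no review | Saved, m = 6 | Saved, m = 5 | Saved, m = 3 |
|---|---|---|---|---|---|
| 15% | 13.73 v 8.40 | 5.33 | 2.45 | 1.86 | 0.95 |
| 5% | 21.67 v 19.20 | 2.47 | 1.10 | 0.84 | 0.45 |
| 2% | 25.23 v 24.44 | 0.79 | 0.40 | 0.30 | 0.16 |

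At 15%, grade 3 IRRs avoided are 0.15 × 1.86 = 0.28 to 0.15 × 2.45 = 0.37.

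**5. One-patient lag.** Suppose one more patient is infused before each outcome is known, and charge this to the new rule only. At 15% the cost is the probability that a planned patient still remained: (1 − p^6) + p^7[1 − p^20 − 20·q·p^19] = 0.623 + 0.264 = 0.887. The savings become 5.33 − 0.89 = 4.44 without review, 1.86 − 0.89 = 0.97 (m = 5), 2.45 − 0.89 ≈ 1.57 (m = 6) and 0.95 − 0.89 = 0.06 (m = 3).

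**6. Type I error and power.** Accrual stops only on paths that end in failure anyway, so the probability of passing in step 1 is the same with or without the sentence.

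**7. Price in estimation.** The mean of the simple proportion over all trials, planned v stopped at the boundary (no review stops in either), is 0.19 v 0.34 at a true 15%, 0.076 v 0.150 at 5% and 0.033 v 0.065 at 2%. Root mean squared error at 15% is 0.11 v 0.36.

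**The case against.** The strongest reply is that nothing is wrong. Looks after 7 and 28 patients define this design, and 12.2 states the rule completely. Section 12.3 already allows an earlier stop. The plan's own expectation is 0 of 148 grade 3 reactions from the third infusion on, so a single event would stand out at a monthly meeting. Stage 1 itself lasts only about 7/6 = 1.2 to 7/5 = 1.4 months. Some delay in knowing the outcome is plausible, since Appendix B counts recurrence after improvement and hospitalization as grade 3. After a stage 1 failure the protocol is to be modified, so a full seven patients would inform that step and the time-savings objective.

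Most of this stands, and it limits the size of the point. It does not close the gap. The review is discretionary and carries no grade 3 count. It is required only monthly, against "With anticipated accrual rate of around 5-6 patients each month". The Data and Safety Monitoring Committee's stated focus is unexpected toxicity, whereas grade 3 IRR is a known reaction (5% of patients in SIRIUS, section 5.2).

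A reader might infer that the design is miscalculated, that the plan obliges accrual to go on after failure, or that about five infusions would be wasted in practice. The documents support none of these. The figures reproduce, 12.3 permits an earlier stop, and the 5.3 is a bound that requires both a true 15% rate and a review that never acts.

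**Conclusion.** The point holds as a cheap improvement, not as a design error: accrual past a determined failure is permitted, though not required. If each outcome is known before the next infusion and a review every 5-6 patients always halts a failed trial, the added sentence saves 1.9-2.5 patients and 0.28-0.37 grade 3 IRRs at a true 15% rate, and 0.3-0.4 patients at 2%. With a one-patient lag the 15% saving is 1.0-1.6 patients, and it is close to nil (0.06) if reviews come every 3 patients. The benefit therefore lies mainly at rates that the plan itself calls unacceptable. Review intervals counted in patients are an assumption; the documents give only a minimum meeting frequency and an anticipated accrual rate.

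**What to change.** Add one sentence to 12.2, for example: *Accrual stops, with the conclusion already stated for that stage, as soon as the first grade 3 IRR at the first accelerated infusion occurs among patients 1-7 or, after 7 of 7 are grade 3 IRR-free, as soon as the second occurs among patients 8-28.* Leave 7/28, the thresholds, the grade 4 rule and the patient management in section 9 unchanged. No new data are needed, because the endpoint is already recorded at each first accelerated infusion.

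The cost falls on a failing trial: a less precise and more upward-biased IRR proportion, and fewer infusions for the time-savings estimate. For example, a stop at patient 4 gives 1/4 = 0.25. With outcomes ordered by stopping point, the exact 95% limits solve 1 − p^4 = 0.025 and p^3 = 0.025, so the interval is 0.006-0.71. One event in a full 7 gives 0.14 (0.004-0.58).

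Report the 12.1 proportion with an exact interval and state that accrual stopped at the boundary. I would not prescribe a median-unbiased estimate. Under the stopping rule its mean is 0.29 at a true 15%, further off than the 0.19 of the planned simple proportion, and it equals 1.0 after a stop at patient 1.
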